## Home Based Virtual Rehabilitation for upper extremity

**Title of Project:**

**Principal Investigator:**

**[name] PT PhD**

**Funding Source(s):**

**NIDILRR #90RE5021-01-00**

**NIH NICHD #1R15HD095403-01A1**

### 1. Purpose/Specific Aims

The overarching aim of this study is to provide a mechanism for patients to engage in progressive motor practice for a meaningful time period. We aim to improve on the positive outcomes found in our work on patients in the chronic phase and the pilot work being done on patients in the acute in-patient phase post stroke to determine whether we can further improve functional recovery using a home based system.

Aim 1: Evaluate compliance with Home-Based Virtually Simulated hand/arm gaming activities and two computer game groups, one with motivation enhanced (ME) simulations and one with non-enhanced (MnE) versions, as compared to compliance with Standard hand/arm home Exercises (HBSE). Hypothesis: Participants in the ME and MnE group will show significant compliance as compared to the control group (HBSE) and the ME group will be superior to the MnE group.

Primary Outcome Measures: For the HBVS group, 1) time on task will be measured by the daily computer file time stamp and 2) amount of moving time will be measured by the actual movement time recorded by the games. For the computer games groups 1) time on task will be measured by recording start and stop time of practice in a notebook and 2) amount of moving time will be measured by commercially available activity monitors.

Aim 2: Evaluate the effectiveness of home-based virtually simulated hand/arm gaming activities (HBVS) for individuals with stroke as compared to a program of standard hand/arm home exercises (HBSE). Hypothesis: Participants completing HBVS training will exhibit significantly improved clinical, kinematic and neurophysiological outcomes as compared to the control group (HBSE).

Primary Outcome Measures for Aim 2: Wolf Motor Function Test, Upper Extremity Fugl-Meyer Assessment of Sensorimotor Recovery after Stroke, Action Research Arm Test, Perception of System Questionnaire, the Stroke Impact Scale, Kinematics, Cortical mapping.

Aim 3: Evaluate the impact of the motivation enhancements designed into computer games to provide a more enjoyable training experience. Hypothesis: Enjoyment of the games will be a more valid predictor of compliance than personal factors.

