## Experimental Design and Training Protocol

### **Aim 1: To test the impact of motivation enhanced, game-based interventions on intrinsic motivation to perform a telerehabilitation exercise program in persons with strokes.**

**Rationale:** Low levels of motivation are cited as the primary barrier to adherence to home based rehabilitation programs. Designing rehabilitation activities that elicit the highest levels of intrinsic motivation is critical to overcoming this barrier and optimizing the effectiveness of home based interventions.

**Hypotheses:** We predict that subjects in the motivation enhanced (ME), game-based intervention group will report higher initial levels of motivation as measured by the Intrinsic Motivation Inventory than those performing un-enhanced control (UC) interventions. We further predict that IMI scores for the ME group will remain higher than those for the UC group.

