**Outcomes Measures:** (See Table 4 for a summary of all measures and Figure 6 for a data collection Schedule). The impact of game mechanics on motivation to perform the simulation that is specifically related to

the experience of using the simulation not the general motivation to improve their hand function or increase their independence, etc. will be measured utilizing the Intrinsic Motivation Inventory (IMI) (58). IMI data will be measured following the first training session (Collection 2) to measure the subjects' initial reaction to the system and simulations as well as after the twelfth session (Collection 3) and after the final training session (Collection 4) to chart subjects' responses to repeated use.

*Statistical Analysis:* (See Table 5 for a summary of all planned comparisons) Our primary outcome measures will compare differences in IMI scores after the initial exposure to the training program. Data will be evaluated for normality and transformed if necessary for evaluation. Baseline group equivalence will be evaluated via t-test. The within-and-between group interaction will be examined to evaluate differences in change between groups.

**Aim 2: To test the impact of intrinsic motivation on adherence to a telerehabilitation exercise program in persons with strokes.**

**Table 4** Outcome measures

Motivation Measure	
Intrinsic Motivation Inventory	Measurement of emotional response to an activity.
Adherence Measures	
Number of interventions days	Recorded by system
Total intervention time	Recorded by system
Average intervention day time	Recorded by system
Clinical Measures	
Upper Extremity Fugl-Meyer Assessment (66)	A 33 item battery which evaluates reflexes, movement patterns in and out of synergy, grasp, and coordination (impairment level)
Action Research Arm Test (62)	19 item battery which tests the ability to handle items of different size, shape and weight (activity level)
Box and Blocks Test (67)	Standardized dexterity test with well-established benchmarks for persons with CVA and age-matched healthy populations
Quality of Life Measure	
Stroke Impact Scale (69)	Patient reported assessment of multiple activity and participation level domains post stroke including hand function, activities of daily living and social participation.
Kinematic/Kinetic Measures	

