Hand opening/closing range of motion	Sum of maximum angular excursions of the paretic metacarpophalangeal (MCP), proximal inter-phalangeal (PIP) and distal inter-phalangeal joints (DIP) joints.
Hand opening velocity	Peak angular velocity during hand opening
Hand trace RMSE	Ability to control hand opening as subject moves a cursor tracking a sine wave. Reported as root mean square error (RMSE) comparing target position and cursor position.
Wrist Trace RMSE	Ability to control wrist flexion and extension as subject moves a cursor tracking a sine wave. Reported as root mean square error (RMSE) comparing target position and cursor position.
Horizontal shoulder and elbow trace RMSE	Ability to control shoulder and elbow as subject moves a cursor tracking a sine wave. Reported as root mean square error (RMSE) comparing target position and cursor position.

*Rationale:* Very few rehabilitation studies examine the interaction between motivation and adherence quantitatively. Utilizing knowledge of this interaction to inform design of rehabilitation simulations should advance the field of home based rehabilitation substantially.

*Hypothesis:* We predict that intrinsic motivation related to game play will predict adherence more effectively than patient readiness alone.

*Subjects:* The same subjects will be utilized for all three aims.

*Outcome measurements:* will include number of sessions as well as total intervention time and average session time. Time signatures from the telerehabilitation system will be used to overcome overestimation effects associated with patient self-reports of actual exercise time (59).

In an attempt to expand our understanding of the interaction between motivation (as measured by the IMI) and adherence to the autonomous home rehabilitation program, we will perform an in depth qualitative analysis focusing on subjects' unique perceptions and understandings of their participation in the proposed rehabilitation program. Using a Grounded Theory approach (60, 61), data collection and analysis will follow

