these steps: 1) A trained interviewer will ask open-ended questions in telephone interviews, allowing participants to reflect on and describe their experiences. 2) Investigators will read participants' narratives to develop a general sense of the subjects' experiences and attitudes toward the rehabilitation program. 3) Investigators will identify emerging narrative themes in participants' experiences and attitudes toward the program. 4) Finally, an iterative coding process will be used to refine initial findings and synthesize these themes.

*Statistical Analysis:* (See Table 5 for a summary of all planned comparisons.) Linear regression will be used to evaluate the effects of IMI (From Data Collection 1) on total time (Collected during training sessions).

**Aim 3: To test the impact of motivation enhanced, game-based interventions on the effectiveness of a telerehabilitation exercise program in persons with strokes.**

*Rationale:* Studies of clinic based interventions targeting hand function in persons with stroke have produced measurable changes in hand function that do not substantially reduce hand related disability. Study of a long term, home based program emphasizing adherence will inform the development of sustainable alternatives to costly clinic based interventions that fall short of the ultimate goal of rehabilitation.

*Hypothesis:* We predict that subjects in the ME group will demonstrate larger improvements in hand function as measured by the Action Research Arm Test (ARAT) than those performing UC interventions. We further predict that subjects in the ME group will demonstrate larger reductions in impairment and larger improvements in measures of motor control and quality of life than UC group subjects.

*Subjects:* The same subjects will be utilized for Aims 1-3.

*Outcome Measures:* (Please see Table 4 for the full listing and description of the proposed clinical and quality of life measures.) A trained RA, blinded to group assignment will collect all outcome measures described in Table 4 immediately prior to training, immediately after training and 3 months after training (Data Collections 1 and 2). The RA will be blinded to previous test scores during post testing and retention testing.

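### As worded in the available SAP text, the Aim 2 regression of total time on IMI cannot test its hypothesis about patient readiness, and its IMI collection number conflicts with the IMI schedule

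*SAP*

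**What the plan says.** **Hypothesis.** The SAP's Aim 2 predicts that "intrinsic motivation related to game play will predict adherence more effectively than patient readiness alone".

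**Analysis.** The Aim 2 Statistical Analysis paragraph points to Table 5 for the planned comparisons and then states: "Linear regression will be used to evaluate the effects of IMI (From Data Collection 1) on total time (Collected during training sessions". It names no other predictor and no comparison of models.

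**Measures.** The available text of SAP Table 4 lists IMI, adherence, clinical, quality-of-life and kinematic measures, but no readiness instrument. The protocol's Aim 3 has a similar comparative hypothesis ("Enjoyment of the games will be a more valid predictor of compliance than personal factors") and names the Patient Activation Measure among its outcomes. Protocol Section 5 plans repeated-measures ANOVA, percent change, recovery curves and published minimum important differences. None of these is a prediction model.

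**IMI timing.** Aim 1, Outcomes Measures, says "IMI data will be measured following the first training session (Collection 2", with later administrations at Collection 3 (twelfth session) and Collection 4 (final session). It defines what IMI captures as "the experience of using the simulation not the general motivation to improve their hand function". Aim 3, Outcome Measures, has the assistant collect "all outcome measures described in Table 4 immediately prior to training, immediately after training and 3 months after training (Data Collections 1 and 2".

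**The concern.** A hypothesis that one predictor does better than another needs both predictors in the analysis. It can mean that IMI adds to readiness, or that IMI beats readiness. A model with IMI as its only predictor tests neither. A significant slope could still be reported as confirming Aim 2, even if readiness explained all of it or predicted adherence better.

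The collection number raises a second, smaller question: which IMI score is the predictor? The cited Collection 1 is not in the IMI schedule. The scheduled collections also differ in how much of the outcome has already accrued when IMI is taken.

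**Working it through.** The documents give no power or sample-size figure for Aim 2, so there is nothing to reproduce. The check is whether the stated test can respond to the stated hypothesis.

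**Inputs.** n = 30 (SAP Aim 1, Subjects), all assumed analysed; two-sided 5% level (assumed for this test). All correlations are assumptions, because the documents give none. T is total time, I is IMI, R is readiness.

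**Step 1: the planned test.** With one predictor, t = r(T,I) × √(n−2) / √(1 − r(T,I)²) on 28 degrees of freedom. The critical t is 2.048, so the slope is significant when |r(T,I)| exceeds 2.048 / √(2.048² + 28) = 0.361. Readiness appears nowhere in this rule.

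**Step 2: what IMI adds to readiness.** This is the partial correlation [r(T,I) − r(T,R) × r(R,I)] / √[(1 − r(T,R)²)(1 − r(R,I)²)], tested on 27 degrees of freedom. It is zero when r(T,I) = r(T,R) × r(R,I).

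**Step 3: rejection rates.** Trivariate normal simulation; the increment column tests IMI given readiness.

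| Scenario | r(T,I) | r(T,R) | r(R,I) | Partial r | IMI-only slope significant | Increment significant |
|---|---|---|---|---|---|---|
| IMI adds nothing | 0.4×0.4 = 0.16 | 0.4 | 0.4 | 0 | 13% | 5% |
| IMI adds nothing | 0.5×0.5 = 0.25 | 0.5 | 0.5 | 0 | 27% | 5% |
| IMI adds nothing | 0.6×0.6 = 0.36 | 0.6 | 0.6 | 0 | 51% | 5% |
| Readiness better | 0.5 | 0.6 | 0.3 | 0.42 | 83% | 64% |
| Readiness better, predictors overlap | 0.5 | 0.6 | 0.8 | 0.04 | 83% | 6% |
| Equal predictors | 0.5 | 0.5 | 0.3 | 0.42 | 83% | 65% |
| IMI better | 0.5 | 0.2 | 0.3 | 0.47 | 83% | 76% |

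The last four rows share r(T,I) = 0.5. The planned test gives 83% in each, whether the hypothesis is true or false. The fourth row also shows a limit of the increment test: IMI can add to readiness (64%) while predicting less well than it.

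**Step 4: comparing the predictors directly.** With r(R,I) = 0.3, a Williams test of the two correlations favours IMI in about 0.5% of trials when readiness is better (0.6 against 0.5), 2.4% when they are equal, and 31% when IMI is better (0.5 against 0.2). It responds to the hypothesis but is weak at n = 30.

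**Step 5: timing.** The SAP's Treatment Protocol prescribes daily practice for twelve weeks: 12 × 7 = 84 sessions. If every session is done, 1/84 = 1.2% precede Collection 2, 12/84 = 14.3% precede Collection 3, and all precede Collection 4.

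**The case against.** **Table 5 is unseen.** The criticised sentence refers to Table 5, which may name a readiness variable or further models; Figure 6 may fix the collection schedule. This stands. A reader might infer that the full SAP has no readiness measure and no comparative test, but the available documents do not support that. Table 4 is weak evidence, since it is captioned as outcomes and readiness would be a baseline predictor. Even so, the Aim 2 sentence does not match its hypothesis and would need aligning with Table 5.

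**The regression has a use.** It does address the broad Aim 2, the link between motivation and adherence. It falls short only of the stated comparison.

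**Arm is also missing.** A reader might infer that omitting arm invalidates the model, because the enhanced group is expected to have higher IMI ("will report higher initial levels of motivation as measured by the Intrinsic Motivation Inventory") and better compliance ("the ME group will be superior to the MnE group"). That goes too far. The SAP intends the enhancements to act through motivation, so conditioning on arm removes some of the variation in IMI that the trial creates. If arm shifts both variables by 0.5 SD with no within-arm link, the IMI-only slope is significant in 6% of trials against 5% with arm in the model; reaching 19% needs a 1.0 SD shift on both.

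**An IMI at Collection 1 can be read from Aim 3.** That sentence literally places every Table 4 measure before training. It would also place system-recorded adherence there, and it gives three time points for two collection numbers, so it does not settle the matter. Nor do the documents show that the trial will use a pre-exposure IMI as predictor. The number is probably a slip for Collection 2.

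**Conclusion.** The point holds for the available text. Followed exactly, the stated regression can neither confirm nor refute the Aim 2 hypothesis. Under the assumed correlations, a significant slope appears in 13% to 51% of trials when IMI adds nothing to readiness, and in about 83% when readiness is the better predictor. The percentages depend on those assumptions and on all 30 subjects being analysed. The logic does not, because readiness does not enter the test.

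The collection-number conflict is real, but on its own it calls only for clarification. It gives no reason to redefine the outcome: if Collection 2 is meant, about 1.2% of scheduled sessions precede the predictor. Confidence is medium, because Table 5 and Figure 6 could supply what is missing.

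**What to change.** 1. **Align hypothesis and model**, by one of two routes.
   - If readiness is collected: regress total time on baseline readiness and IMI, compare this with the readiness-only model, and test the IMI increment. Claim that IMI adds to readiness. Claim that it predicts better only if the two predictors are compared directly, and describe that estimate as imprecise at n = 30. The protocol's Patient Activation Measure can serve if the sponsor confirms that it is the readiness measure and is taken at baseline; the SAP should then list it.
   - If no readiness measure is collected: restate the Aim 2 hypothesis as an association between IMI and total intervention time.
2. **Reconcile the collection numbers** in the Aim 1 Outcomes Measures and Aim 2 Statistical Analysis paragraphs, and name the IMI administration used as predictor.
3. If Table 5 already contains these terms, align the Aim 2 sentence with it.

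Keep total time as the outcome. An arm-adjusted model may be reported as a sensitivity analysis.

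**Cost.** Possibly one baseline questionnaire, and one further degree of freedom. With assumed correlations with time of 0.5 (IMI) and 0.2 (readiness), no arm effect, and 0, 0.3 or 0.5 between the predictors, the partial correlations are 0.5/√0.96 = 0.51, 0.44/√(0.96×0.91) = 0.47 and 0.40/√(0.96×0.75) = 0.47. The increment test then has about 83%, 76% or 76% power, against 83% for the IMI-only slope. Restating the hypothesis costs only the wording.

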**Subjects:** This will be a randomized, blinded study. The same subjects will be utilized for all three aims. Upon IRB approval 30 persons with chronic strokes will be recruited from the outpatient rehabilitation department of JFK Medical Center, its hospital based fitness center program for persons with stroke and its stroke support group. **Inclusion criteria** are a) 25-85 years old, b) unilateral stroke, c) score of 24 or greater on the Folstein Mini-Mental Status Exam(52), d) Score of 1 or better on extinction and inattention portion of NIH Stroke Scale (NIHSS)(53), e) Fugl-Meyer (FM) between 30-60/66 (54), f) Score of 1 or better on language portion of NIHSS, g) intact cutaneous sensation (e.g. ability to detect <4.17N stimulation using Semmes-Weinstein nylon filaments(55). **Exclusion criteria are:** Orthopedic issues that would limit the ability to perform regular upper extremity activity. **Randomization:** Because level of impairment may affect (a) compliance with training regime, (b) intrinsic motivation, (c) adherence, and finally (d) measures of effectiveness, it is crucial (especially in a study with limited n) to balance the treatment and control arms. Because simple randomization of subjects to arms may not result in a balanced design, and because the ability to statistically adjust for baseline arm differences in these two characteristics is likely to be limited, we will use the following strategy to ensure arm equivalency. Subjects' initial scores on our measurement of motor control impairment caused by the stroke the (UEFMA) will be dichotomized into low/high. Subjects are then classified into the cell corresponding to their impairment level. Subjects in each cell (n1, n2) are provided random IDs (to prevent an ID by case recruitment association), and an investigator blinded to the randomization process then randomly assigns the first case in each cell to treatment or control arm. Each following subject within the cell is then assigned sequentially to the alternate arm. This is done for all cells to balance the source of variability between arms. **Blinding: Subjects** will be blinded to the purpose of the study and group assignment. They will also be blinded to their previous self-reported scores and their previous performance on objective tests. **Research assistants** performing outcomes measures will be blinded to group assignment and blinded to previous performance on all tests.

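### The SAP Aim 2 regression names IMI as its only predictor of practice time, so its slope may be confounded by impairment; pre-specify continuous baseline UEFMA as a covariate

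*SAP*

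**What the plan says.** The SAP's Aim 2 statistical analysis paragraph refers to Table 5 for the planned comparisons and then gives one sentence of method: "Linear regression will be used to evaluate the effects of IMI (From Data Collection 1) on total time (Collected during training sessions". IMI is the only predictor in it. Table 5 is not in the text available for this review.

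The randomization paragraph under SAP Aim 1, which covers the same subjects, explains why impairment needs attention: "Because level of impairment may affect (a) compliance with training regime, (b) intrinsic motivation, (c) adherence". The remedy it gives is in the allocation. The subjects' "initial scores on our measurement of motor control impairment caused by the stroke the (UEFMA) will be dichotomized into low/high", and cases alternate between arms within each cell: "This is done for all cells to balance the source of variability between arms". On modelling, it says only that "the ability to statistically adjust for baseline arm differences in these two characteristics is likely to be limited".

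Two further facts matter. Eligibility is "Fugl-Meyer (FM) between 30-60/66", so impairment still varies among those enrolled. The sample is small: "Upon IRB approval 30 persons with chronic strokes will be recruited".

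**The concern.** Items (b) and (c) of the SAP's list are the Aim 2 predictor and outcome. A variable that may affect both is a possible common cause. If less impaired subjects both enjoy the games more and play for longer, IMI and total time will correlate even if motivation has no effect on practice.

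Allocation does not prevent this. Alternating within UEFMA cells makes the two arms alike in impairment. Aim 2 compares subjects with high and low IMI, whichever arm they are in, and nothing in the design makes those subjects alike in impairment.

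Aim 2 is worded as a question about the impact of motivation on adherence, and the analysis sentence speaks of effects. It is the only quantitative test of that question described in the available SAP text; the interviews are qualitative. A positive slope from the model as worded could not be separated from an impairment effect that the SAP itself considers possible.

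**Working it through.** The plan gives no power, effect size or correlation for this regression, so there is no stated figure to reproduce.

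**Inputs**
- n = 30 (SAP, Subjects).
- Significance level 0.05 (Protocol 3.3; the available SAP text gives none). Two-sided testing is an assumption.
- a = correlation of UEFMA with IMI, b = correlation of UEFMA with total time. Neither is in the documents. Both are assumed, and a range is shown.
- True effect of IMI on time: zero.

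**Step 1: induced correlation.** Let Z be standardized UEFMA, IMI = aZ + √(1−a²)·e₁ and time = bZ + √(1−b²)·e₂, with independent errors. Then corr(IMI, time) = a·b although no path runs from IMI to time. Given Z, the partial correlation has numerator ab − a·b = 0.

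**Step 2: approximate rejection rate.** With the Fisher transformation, δ = atanh(ab)·√(30−3) = 5.196·atanh(ab), and the rate is P(N > 1.96 − δ) + P(N < −1.96 − δ).
- a = b = 0.3: ab = 0.09, δ = 0.469, rate = 0.068 + 0.008 = 0.076.
- a = b = 0.5: ab = 0.25, δ = 1.327, rate = 0.263 + 0.001 = 0.264.

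**Step 3: simulation.** 40,000 samples of 30 per row, t-test of the IMI slope:

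| a = b | induced r | IMI only | + continuous UEFMA | + low/high UEFMA |
|---|---|---|---|---|
| 0.1 | 0.01 | 4.9% | 5.0% | 5.0% |
| 0.2 | 0.04 | 5.6% | 5.0% | 5.2% |
| 0.3 | 0.09 | 7.8% | 5.0% | 5.4% |
| 0.4 | 0.16 | 13.6% | 5.2% | 6.4% |
| 0.5 | 0.25 | 26.8% | 4.9% | 8.7% |

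Repeat runs with other seeds agree to within about one percentage point. If impairment is related to only one of the two variables, the IMI-only rate stays at about 5% (4.9% with a = 0.3, b = 0; 5.2% with a = 0, b = 0.5). With opposite signs (a = −0.5, b = 0.5) it is 26.7% and the spurious slope is negative. The low/high split was taken at the median; it leaves part of the confounding in place because impairment still varies within each half.

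**Step 4: price of the adjustment.** Residual degrees of freedom fall from 28 to 27. The variance inflation factor for the IMI slope is 1/(1−a²): 1/0.91 = 1.10 at a = 0.3 and 1/0.75 = 1.33 at a = 0.5. The standard error therefore grows by a factor of at most √1.10 = 1.05 to √1.33 = 1.15, and by less if UEFMA also explains variation in time.

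**Step 5: limit of the adjustment.** Suppose arm, balanced on UEFMA, is a second common cause. Let u be the correlation of UEFMA, and v that of arm, with each of IMI and time. The IMI–time correlation left after UEFMA adjustment is v²/(1−u²).
- u = v = 0.3: 0.09/0.91 = 0.10, rejection about 8%.
- u = v = 0.4: 0.16/0.84 = 0.19, rejection about 17%.
- u = 0.2, v = 0.4: 0.16/0.96 = 0.17, rejection about 14%, against 19% with IMI alone.

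**The case against.** Several points can fairly be made against this.

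- *The SAP says only that impairment may have these effects.* This stands. A reader might infer that the slope is confounded and that the SAP says so. It does not: it names a possibility, as a reason for balancing arms.
- *Table 5 might list covariates.* This also stands. A reader might infer that the whole plan leaves impairment out, but only the analysis sentence can be shown to do so.
- *The design may weaken the link between impairment and IMI.* Games are calibrated to each subject's range of motion, therapists individualize settings, arm support is tuned to a success band usually of 70% to 85%, difficulty adapts in the control group, and Fugl-Meyer is restricted to 30 to 60. These features make small correlations plausible, and at 0.2 or below there is almost no inflation. They do not show that the correlations are small, and they act less directly on any link between impairment and playing time.
- *The hypothesis is about prediction.* Aim 2 predicts that IMI will do better than patient readiness, and confounding matters less for prediction. This stands in part, but the aim title and the analysis sentence are causal, and the rationale is to inform game design. Patient readiness is missing from the model as worded; UEFMA adjustment does not address that.
- *The SAP doubts the value of statistical adjustment.* That remark concerns baseline differences between arms. One continuous covariate with 30 subjects is affordable.
- *UEFMA is not the only possible common cause.* This stands. Aim 1 expects arm to change IMI, and leaderboards and avatars could change playing time directly. It limits what the adjustment achieves; it does not make the unadjusted slope preferable.

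**Conclusion.** The concern holds in conditional form: as worded in the available text, the Aim 2 slope may be confounded by impairment, and arm balance does not prevent that. How much this matters rests on two correlations that the documents do not give. It is negligible if both are 0.2 or less or if either is zero, modest at 0.3, and serious from about 0.4 upward.

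It would go too far to conclude that a significant slope will be spurious, or that adding UEFMA guarantees a 5% error rate. The return to 5% in the simulation assumes that UEFMA is the sole common cause, is related linearly to IMI and time, and is measured without error. The change is still worth making: the SAP has already named this variable as a possible influence on both sides of the regression, it is collected before allocation, and adjusting for it costs almost nothing. Trial conduct is unaffected.

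**What to change.** In the SAP Aim 2 statistical analysis paragraph, pre-specify the model total time = IMI + baseline UEFMA, with UEFMA as a continuous score and not the low/high allocation split. Base the Aim 2 conclusion on the adjusted IMI slope with its 95% CI, and report the unadjusted slope beside it so that the change is visible. State that the adjustment covers measured impairment only. If other common causes are considered plausible, treatment arm first among them, give each its own pre-specified term. If Table 5 already lists UEFMA for this comparison, bring the paragraph into line with it.

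The same edit should settle which IMI measurement enters the model: this paragraph takes it from Data Collection 1, while the Aim 1 outcome paragraph first measures IMI at Collection 2.

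Cost: one or two sentences, one degree of freedom (one more for each added term), and an IMI slope variance up to about 1.1 to 1.3 times as large at UEFMA–IMI correlations of 0.3 to 0.5. No new data, visits or subjects are needed.

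### The visible Aim 2 regression of practice time on IMI has no arm term, so part of its slope can reflect assigned arm rather than motivation

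*SAP*

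**What the plan says.** The visible statistical text for SAP Aim 2 is a pointer to Table 5 and one sentence: "Linear regression will be used to evaluate the effects of IMI", with total time during training as the outcome. It names one predictor and one outcome. It mentions no arm term, arm interaction, by-arm analysis or other covariate. Section 5 of the Protocol describes a repeated-measures analysis of variance and no regression, so it does not fill the gap.

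The analysis set covers both arms: "The same subjects will be utilized for all three aims". The size comes from the Subjects paragraph under SAP Aim 1: "Upon IRB approval 30 persons with chronic strokes will be recruited". Allocation is close to 1:1, because within each impairment cell "Each following subject within the cell is then assigned sequentially to the alternate arm".

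The documents expect arm to affect both variables:

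- **Arm and IMI.** SAP Aim 1 predicts that the enhanced group "will report higher initial levels of motivation as measured by the Intrinsic Motivation Inventory than those performing un-enhanced control (UC) interventions".
- **Arm and practice.** Aim 1 in Section 1 of the Protocol predicts, for compliance, that "the ME group will be superior to the MnE group".

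On timing, the Outcomes Measures paragraph of SAP Aim 1 places the first IMI after the first training session and calls it Collection 2. The Aim 2 regression takes IMI from Data Collection 1.

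**The concern.** Arm is fixed by randomisation before any IMI is taken and before practice time accrues. If arm moves both, a regression that pools the arms mixes two things: the association between IMI and time among people playing the same version of the games, and the difference between the two arm means. Only the first bears on whether a more motivated person practises more.

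The design offers a plausible route from arm to time that a first-session IMI may miss. Under the SAP's Treatment Protocol, the enhanced arm gets changing level graphics, growing scoring opportunities, a leaderboard with career scores, and new avatars at career-score milestones. The control arm gets none of these. They build up over twelve weeks, whereas the first IMI records a reaction to one session.

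Aim 2 asks about the effect of intrinsic motivation on adherence, and its rationale is to guide the design of rehabilitation games. A slope generated partly by the arm difference would support that conclusion for the wrong reason. The exposure is greatest when the enhanced games work well on both variables.

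**Working it through.** The documents give no power, slope or sample-size figure for this regression, so there is no planned figure to reproduce. The check asks what the pooled slope estimates.

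**Inputs from the documents.** N = 30 (SAP, Subjects), taken as 15 per arm under near 1:1 allocation.

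**Assumptions.** A two-sided 0.05 test: Protocol 3.3 gives 0.05 for the Wolf test, but no level is stated for this regression. Arm effects are varied from 0 to 1.2 SD because neither document gives a size.

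**Model.** Scale IMI and time to within-arm SD 1. Let d1 be the arm shift in IMI, b the within-arm slope of time on IMI, and g the arm effect on time that does not pass through IMI. The total arm shift in time is d2 = b·d1 + g. With equal arms:

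- variance of pooled IMI = 1 + d1²/4
- covariance of pooled IMI and time = b + d1·d2/4 = b(1 + d1²/4) + g·d1/4
- pooled slope = b + (g·d1/4)/(1 + d1²/4)

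The second term is the bias. It is zero if g = 0 (arm acts on time only through IMI) or if d1 = 0 (arm does not move IMI).

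**Case of no motivation effect (b = 0, so g = d2).** The pooled correlation is r = (d1·d2/4)/√[(1 + d1²/4)(1 + d2²/4)]:

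- 0.5 and 0.5: 0.0625/1.0625 = 0.06
- 0.8 and 0.5: 0.10/√(1.16 × 1.0625) = 0.09
- 0.8 and 0.8: 0.16/1.16 = 0.14
- 1.0 and 1.0: 0.25/1.25 = 0.20
- 1.2 and 1.2: 0.36/1.36 = 0.26

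Rejection rates for the IMI slope, from 40,000 simulated trials per setting:

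| d1 (IMI) | d2 (time) | pooled r | without arm | with arm |
|---|---|---|---|---|
| 0 | 0.8 | 0 | 5.0% | 5.0% |
| 0.8 | 0 | 0 | 4.8% | 4.9% |
| 0.2 | 0.2 | 0.01 | 5.1% | 5.0% |
| 0.5 | 0.5 | 0.06 | 6.1% | 5.0% |
| 0.8 | 0.5 | 0.09 | 7.6% | 5.1% |
| 0.8 | 0.8 | 0.14 | 11.4% | 5.2% |
| 1.0 | 1.0 | 0.20 | 18.7% | 5.1% |
| 1.2 | 1.2 | 0.26 | 30.4% | 5.1% |

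**Case of full mediation (g = 0, d1 = 0.8).** Both models recover the slope: mean 0.300 without arm and 0.299 with it for b = 0.3, and 0.499 in both for b = 0.5. Here the arm term only costs precision. Variance inflation is 1 + d1²/4 = 1.16. Power falls from 42% to 36% at a within-arm correlation of 0.3, and from 87% to 81% at 0.5.

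**Time point.** The bias needs d1 ≠ 0, hence an IMI taken after exposure to the assigned games. Aim 2 says Data Collection 1. Aim 1 says the first IMI is Collection 2, after session one. Aim 3 lists pre-training, post-training and three-month assessments but labels them Data Collections 1 and 2, which suggests that Collection 1 precedes training. Aim 1 describes the IMI as measuring the experience of using the simulation and schedules none before training. The Aim 2 label is therefore probably wrong, but the text supplied cannot settle it.

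**The case against.** The strongest reply is that the SAP's implied chain runs from enhancements to motivation to adherence. Leaderboards, levels and avatars are listed in SAP Table 2 as the motivational enhancements themselves, and the IMI is there to register their effect. If that chain is complete, the pooled slope is unbiased, and adjusting for arm discards IMI variation that the design deliberately creates. The algebra bears this out. Neither document predicts a direct arm effect on time; the Protocol hypothesis is about the total effect on compliance, in a design that also has a standard-exercise group. What does not follow is that an IMI taken after one session carries the whole effect of rewards that accumulate over twelve weeks. The SAP itself repeats the IMI after the twelfth and final sessions to follow how responses change.

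A reader might infer that the SAP definitely omits arm. The documents do not support that. Table 5, cited in the same paragraph for all planned comparisons, is not in the text supplied, so the most that can be said is that the visible text mentions no arm term.

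A reader might also infer that a spurious motivation finding is to be expected. That is not supported either: it requires a post-exposure IMI and an arm effect on time outside IMI, and at modest effects the excess is small.

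It is also fair to object that Aim 2's hypothesis compares IMI with patient readiness, and the visible model has no readiness term. That is a separate gap, which an arm term does not close.

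**Conclusion.** The concern holds as a conditional one. On the visible text, the Aim 2 slope can partly reflect arm rather than motivation, provided that IMI is measured after exposure to the assigned games and arm affects time by some route outside measured IMI. The first condition matches the SAP Aim 1 schedule; the second is plausible from the design but is not stated in the documents.

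The size depends on assumed arm effects. The excess over 5% is slight up to shifts of 0.8 SD in IMI and 0.5 SD in time, and becomes material when both are 0.8 SD or more. The 30% figure is the far end of the range: it needs 1.2 SD on both variables, no within-arm association, and an effect on time that bypasses IMI entirely. It should not be read as the expected error rate. The point merits a change because the protection is simple and its cost is known, not because a large error has been shown.

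**What to change.** - Check Table 5. If it already includes arm, state that in the Aim 2 text.
- Otherwise, prespecify total time regressed on IMI and randomised arm, with the arm-adjusted IMI slope as the Aim 2 result and the unadjusted slope as supportive. If the two differ, the difference shows how much the pooled estimate owes to the contrast between arms.
- Reconcile the IMI time point between Aim 2 (Data Collection 1) and Aim 1 (Collection 2), and state which IMI enters the model.

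The cost is more than the one degree of freedom. If arm shifts IMI by 0.8 SD, the variance of the IMI slope rises by a factor of about 1.16, so its standard error rises by about 8% (√1.16 = 1.08). Under full mediation that means about 6 points of power. If arm shifts IMI by 0.5 SD, the factor is only 1.06. No extra data are needed.
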